## **9. STUDY PROCEDURES**

Once the investigational site is activated for study participation, subjects may be enrolled if they have met the inclusion criteria in Section 8.1 and have not been excluded based on the exclusion criteria in Section 8.2.

### **9.1. Screening, Enrollment and Randomization**

Subjects must be consented before any screening tests or assessments are performed. At the time of consent, the subject will be enrolled into the study.

Subjects will be initiated on daclizumab after all screening assessments have been completed and after the Investigator has verified that they are eligible per criteria in Sections 8.1 and 8.2. No subject may begin treatment prior to registration and assignment of a unique subject identification number. Any subject identification numbers that are assigned will not be reused even if the subject does not receive treatment. If an eligible subject was approached and did not participate in the study, the reason for nonparticipation will be documented in the screening log

### **9.2. Follow-Up**

Subjects will be followed-up for 12 months with assessments at Months 1, 3, 4, 6, 9, and 12. There will be a 4-month safety visit conducted remotely. The follow-up study assessments are described in Section 11.2.

Subjects having tentative disability progression identified near the end of the core study (e.g., Month 12) will attend additional follow-up visits 12 and 24 weeks later to confirm progression.

Subjects who do not receive a treatment dose for 2 or more consecutive months will continue to be followed for data collection.

### **9.3. Withdrawal of Subjects from the Study**

Subjects must be withdrawn from the study for any one of the following reasons:

- The subject withdraws consent.
- The subject is unwilling or unable to comply with the protocol.
- The Investigator withdraws the subject from the study for medical reasons.

The reason for the subject's withdrawal from the study must be recorded in the subject's case report form (CRF).

Subjects who withdraw from the study will not be replaced.

CONFIDENTIAL

The information contained herein may not be used, disclosed, or published without the written consent of  
Biogen MA Inc.

## **10. STUDY TREATMENT**

Biogen MA Inc. will provide daclizumab to sites in the US. Biogen Idec Research Limited will provide daclizumab to sites in all other countries. Daclizumab must be administered on-site during the first 6 months, and at the Month 9 visit. Sites have the option to allow subjects to administer the drug at home for doses at Month 7, 8, 10, and 11.

### **10.1. Dosing Regimen and Administration**

Refer to and follow the prevailing local labeling, directions for handling and administration (DHA) and Investigator Brochure.

Daclizumab is supplied as a sterile, preservative-free, colorless to slightly yellow, and clear to slightly opalescent liquid. The drug product is supplied in a single-use pre-filled pen, also known as an autoinjector, in this study. Daclizumab is supplied as 150 mg of daclizumab per 1.0 mL and is administered SC once a month.

As shown in the study schematic, doses at Months 7, 8, 10 and 11 can be administered either at home or supervised at the site. Therefore, at Months 6 and 9, subjects choosing to self-administer at home will be provided with 2 kits to take home along with cool bags and sharp bins.

Subjects should be trained in the proper technique and storage for self-administering SC injection using the autoinjector. The usual sites for SC injection include the thigh, abdomen, and back of the upper arm.

Each daclizumab autoinjector is provided with the needle pre-attached. Autoinjectors contain a single dose only and should be discarded after use. Once removed from the refrigerator daclizumab should be allowed to warm to room temperature (about 30 minutes) prior to injection. External heat sources such as hot water must not be used to warm daclizumab. The daclizumab autoinjector must not be used if the liquid is cloudy or contains floating particles. The liquid must be colorless to slightly yellow.

### **10.2. Treatment Compliance**

Compliance with at-home treatment dosing is to be monitored and recorded by subjects. Beginning with the Month 7 visit when at-home, self-administered treatment can be initiated, self-reported subject adherence to treatment along with MS treatment information will be captured using a dosing diary, for subjects who self-administer. The dosing diaries will be provided at the Month 6 and Month 9 visits, and will be reviewed periodically by study site staff and the Clinical Monitor. The provided drug kits will be individually numbered in order to help with tracking of any compliance differences between doses administered at home and in the clinic.

In the event that a dose is missed and less than 2 weeks have passed since the date the missed dose was originally scheduled, subjects should be instructed to inject their missed dose as soon as it is remembered and remain on their original monthly dosing schedule. If a dose is missed and more than 2 weeks have passed from the date the missed dose was originally scheduled,

CONFIDENTIAL

The information contained herein may not be used, disclosed, or published without the written consent of Biogen MA Inc.

subjects should skip the missed dose, wait to dose again until their next scheduled dose, and then remain on their original monthly dosing schedule. Only 1 dose should be administered at a time.

### **10.3. Daclizumab Stability and Storage**

Daclizumab will be supplied as a solution for injection, in the autoinjector. In addition to the active ingredient daclizumab, the solution includes the following excipients: sodium succinate anhydrous (5.94 mg), succinic acid (0.35 mg), sodium chloride (5.84 mg), polysorbate 80 (0.30 mg), water for injection, and 0.14 mmol sodium per dose.

The label includes conditions for storage, lot number, and other pertinent information such as Sponsor and caution statement.

Study treatment must be stored in a secure location. Accountability for study treatment is the responsibility of the Investigator. More details concerning this responsibility are included in Section 10.4.

Study treatment must only be dispensed by a Pharmacist or appropriately trained staff. Study treatment is to be dispensed only to subjects enrolled in this study.

Study site staff should refer to the Investigator Brochure and/or Product Leaflet for specific instructions on the handling, preparation, administration, and disposal of the study treatment

#### **10.3.1. Daclizumab Preparation**

The individual administering daclizumab should first carefully review instructions provided in the prevailing local labeling, DHA, and Information for Patients (if subjects are self-administering) or Investigator's Brochure (for Investigators administering treatment). If kit packaging is damaged, or if there is anything unusual about the appearance or attributes of the pen device, it should not be used. The kit or pen in question should be saved at the study site, and the problem immediately reported to Biogen.

Daclizumab is to be stored in controlled refrigeration between 2°C to 8°C (36°F to 46°F) in the closed original carton to protect from light. If needed, daclizumab may be stored without refrigeration up to 30°C (up to 86°F) for up to 30 days. The daclizumab pen should not be placed back into the refrigerator after warming to room temperature. It should not be frozen or exposed to high temperatures. For the most up-to-date storage requirements, follow the instructions provided in the approved package insert

#### **10.3.2. Daclizumab Handling and Disposal**

The Investigator must destroy all unused pens of daclizumab as instructed by Biogen.

### **10.4. Daclizumab Accountability**

Accountability for study treatment is the responsibility of the Investigator. The study site must maintain accurate records demonstrating dates and amount of study treatment received, to whom dispensed (subject-by-subject accounting), and accounts of any study treatment accidentally or deliberately destroyed or lost.

CONFIDENTIAL

The information contained herein may not be used, disclosed, or published without the written consent of Biogen MA Inc.

Unless otherwise notified, all type of packaging both used and unused must be saved for study treatment accountability. Subjects self-administering daclizumab at home will be provided with sharps bins for disposal of packaging. Subjects must bring sharps bins with them to clinic visits for accountability. At the end of the study, reconciliation must be made between the amount of daclizumab supplied, dispensed, and subsequently destroyed or returned to Biogen. A written explanation must be provided for any discrepancies.

If any study treatment supplies are to be destroyed at the site, the Principle Investigator(s) must obtain prior approval by Biogen. The Principle Investigator(s) must notify Biogen, in writing, of the method, date, and location of the destruction.

## **10.5. Treatment Schedule Modification**

Subjects who experience a significant change in their medical status (e.g., neurological worsening/suspected MS relapse, possible injection-site reaction, infection, cutaneous event, fever, abdominal pain, persistent diarrhea, jaundice, nausea, vomiting, pruritus) must contact the Study Neurologist as soon as possible and no more than 48 hours after symptom onset. The subject should then be evaluated by the Study Neurologist within no more than 72 hours for physical and neurological assessments and further treatment recommendations if appropriate. These subjects should not administer additional daclizumab until they have been evaluated by the Study Neurologist or their backup

### **10.5.1. Elevated Liver Function Tests**

LFT procedures are described in Section 11.3.2. Prior to starting treatment with daclizumab, serum transaminases (ALT and AST) and bilirubin levels must be obtained. Serum transaminases must be monitored monthly during treatment and up to 4 months after the last study dose of daclizumab (see Section 4.2, for timing).

Study treatment must be temporarily suspended if a subject develops any of the following:

- ALT/SGPT, or AST/SGOT  $>3*ULN$ .
- ALT or AST have not exceeded 5 times the ULN; daclizumab may be resumed when ALT or AST have reached  $<2$  times the ULN.
- Any other clinically significant hepatic condition in the opinion of the Investigator including jaundice.

Note: For subjects who present with jaundice, an LFT must be performed as soon as possible. After a suspension, dosing of daclizumab may be resumed when ALT/SGPT and AST/SGOT are  $<2*ULN$  provided that the criteria for permanent discontinuation have not been met.

Study treatment must be permanently discontinued if a subject develops any of the following:

- Confirmed ALT or AST of  $>5$  times the ULN ALT/SGPT or AST/SGOT  $>3*ULN$  with concomitant elevation of total bilirubin  $>2*ULN$ .
- If a subject has treatment suspended for an LFT elevation and has also had a prior treatment suspension for an LFT elevation during daclizumab use, daclizumab must be permanently discontinued unless an alternative explanation for the LFT elevation unrelated to daclizumab use is clearly identified by the Investigator.

CONFIDENTIAL

The information contained herein may not be used, disclosed, or published without the written consent of Biogen MA Inc.

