## 4.2. Schedule of Assessments

The schedule of assessments is presented in [Table 1](#). Assessment time points include an enrollment visit, a baseline visit, and follow-up visits at Months 1, 3, 4, 6, 9 and 12. An additional safety assessment will be performed remotely 4 months after the last study treatment dose. Subjects who discontinue treatment early will still be evaluated during the safety follow-up visit (i.e., 4 months after treatment and study discontinuation). Subjects having tentative disability progression identified near the end of the core study (e.g., Month 12) will attend additional follow-up visits 12 and 24 weeks later to confirm progression.

Magnetic resonance imaging (MRI) scans will be performed at the enrollment visit (no later than 7 days prior to the first dose of daclizumab), and at Months 1, 4, 6 and 12. MRI scans will be performed under the supervision of a trained radiologist. Ad-hoc MRI scans may be performed as needed, such as in the event of a MS relapse, in order to rule out a progressive multifocal leukoencephalopathy (PML) diagnosis.

Blood chemistry and hematology assessments will be performed at baseline and at Months 1, 3, 6, 9 and 12. Hematology assessments will include a complete blood count (CBC). Liver function tests (LFT) [alanine transaminase (ALT)/ aspartate transaminase (AST)] will be done at enrollment and monthly visits. Bilirubin testing must be done together with the first AST/ALT test at the enrollment visit. Bilirubin testing must also be done if ALT/SGPT (serum glutamic pyruvate transaminase), or AST/SGOT (serum glutamic oxaloacetic transaminase)  $>3*$ upper limit of normal (ULN), since treatment must be permanently discontinued with the concomitant elevation of total bilirubin  $>2*ULN$ .

At the end of the study, liver monitoring will be done per routine clinical practice.

A safety follow-up visit at 4 months after the last dose of daclizumab provided by the study will be conducted remotely to evaluate potential delayed safety outcomes. The assessments during the additional safety follow-up period will include all safety endpoints described in [Table 1](#). Liver function tests (LFT) will be performed only if the subject is continuing daclizumab or if the subject is within 4 months since study treatment discontinuation, and monitoring is deemed appropriate by the Investigator.

CONFIDENTIAL

The information contained herein may not be used, disclosed, or published without the written consent of  

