## Efficacy and Safety of Daclizumab in Subjects with RRMS Switching from Natalizumab

1. Written informed consent must be obtained prior to start of the study.
2. Screening MRI should occur no later than 7 days prior to the first dose of daclizumab. For subsequent visits, MRI scan can be performed up to 4 days prior to the visit. Ad-hoc MRIs may be conducted as needed, such as in the event of a relapse to rule out PML diagnosis.
3. This is required only for females of child-bearing potential. A urine pregnancy test will be performed monthly.
4. Liver function tests (LFTs) are required to be performed monthly (either on-site or via home visits at Month 7, 8, 10 and 11, if applicable), and samples will be analyzed centrally for the purposes of this study. Results from either local or central LFT tests can be used for medical management of the patient and to determine whether dosing should continue or be suspended at the monthly dosing timepoint. In cases where local LFTs were performed, samples must also be collected for central analysis.
5. Liver function tests (LFTs) during the safety follow-up will be performed only if the subject is continuing daclizumab or if the subject is within 4 months since study treatment discontinuation, and monitoring is deemed appropriate by the Investigator; Abnormal AST/ALT values as described in the product label will lead to treatment suspension or discontinuation.
6. [REDACTED]
7. Samples will be analyzed centrally.
8. Daclizumab dosing will start at baseline and occur monthly until Month 11. Doses at baseline and Months 1, 2, 3, 4, 5, 6 and 9 will be administered in the clinic, and doses at Months 7, 8, 10 and 11 can be administered at home or in the clinic. Daclizumab dosing will not begin until a minimum of 28 days have passed since last natalizumab dose. Before a monthly dose of daclizumab is given, LFT results from a prior test performed within the previous 28 (+3) days must be reviewed by the Study Neurologist or their backup.
9. Subjects will be provided a dosing diary at the Month 6 and Month 9 visits to record observations for home dosing only; home dosing is possible for Month 7, 8, 10, and 11. A window of  $\pm 4$  days applies to daclizumab dose even if it is done at home; subjects should be appropriately instructed on daclizumab self-administration using the autoinjector.

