#### 11.2.2.2. Laboratory Assessments

As per Section 11.3.2, a central laboratory will perform laboratory analyses and provide reference ranges for each test.

Laboratory assessments will include the following:

- CBC including hemoglobin, hematocrit, platelet count, red blood cell count and white blood cell count (with differential).
- Blood chemistry including sodium, potassium, chloride, total bilirubin, alkaline phosphatase, lactate dehydrogenase, gamma glutamyl transferase, blood urea nitrogen, creatinine, and bicarbonate and bilirubin.
- [REDACTED]
- [REDACTED]
- [REDACTED]
- [REDACTED]
- LFT including ALT/SGPT, AST/SGOT, and bilirubin:
  - LFT is to be conducted monthly in a blood draw conducted.
  - LFT will be performed only if the subject is continuing daclizumab or if less than 4 months have passed since the subject discontinued treatment and monitoring is deemed appropriate by the Investigator.

Refer to Section 4 for the timing of assessments.

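### Liver function tests after the last daclizumab dose are required in Protocol Section 10.5.1 but left to the Investigator's judgement in Section 4.2, Table 1 footnote 5 and Section 11.2.2.2

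*Protocol*

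**What the plan says.** Two places read as a requirement:

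- Protocol Section 10.5.1: "Serum transaminases must be monitored monthly during treatment and up to 4 months after the last study dose of daclizumab". It points to Section 4.2 for timing.
- Protocol Section 7.2: subjects who stop treatment are followed for a further 4 months, and LFT is among the data to be collected. No discretion clause is attached.

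Three places make the tests conditional:

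- Protocol Section 4.2: in the safety follow-up, LFTs are done only if the subject is still on daclizumab or is "within 4 months since study treatment discontinuation, and monitoring is deemed appropriate by the Investigator".
- Table 1 footnote 5, attached to the Month 15 entry: "Liver function tests (LFTs) during the safety follow-up will be performed only if the subject is continuing daclizumab", or under the same 4-month and Investigator condition.
- Protocol Section 11.2.2.2: off treatment, LFTs are done only if "less than 4 months have passed since the subject discontinued treatment and monitoring is deemed appropriate by the Investigator".

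Section 4.2 adds a further sentence: "At the end of the study, liver monitoring will be done per routine clinical practice".

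On timing, Table 1 footnote 8 says "Daclizumab dosing will start at baseline and occur monthly until Month 11". The safety follow-up is remote, set at 4 months after the last dose, and labelled Month 15 (±14 days).

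**The concern.** The cross-reference in Section 10.5.1 does not settle the matter, because it leads to the text that conflicts with it. Two sites can each follow the protocol and test differently: one draws blood because Section 10.5.1 obliges it to, the other does not because Section 4.2 allows the Investigator to decide.

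What is at stake is even ascertainment of transaminase elevations after the last dose. Section 4.2 gives the detection of delayed safety outcomes as the purpose of the follow-up visit, and Section 5.1.4 reports elevations above 5 times the upper limit of normal (ULN) in 6% of daclizumab subjects against 3% on the comparator in the second pivotal trial. If testing depends on local judgement, the results obtained come from a selected subset. The early termination makes this window more prominent: SAP Section 2 bases the abbreviated report on data available at the market withdrawal and from the safety follow-up.

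**Working it through.** No error rate or sample size bears on this point. The check is schedule arithmetic plus a comparison of passages.

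**Inputs.** Last dose at Month 11 (Table 1 footnote 8). Safety follow-up 4 months after the last dose (footnote 13), ±14 days. Month 12 visit ±4 days. LFT row of Table 1: entries at Month 12, at Month 15 (conditional, footnote 5) and at early discontinuation. Off-visit sampling: Months 7, 8, 10 and 11 are the months named in footnote 4 and Section 11.3.2. One month is taken as 365.25/12 = 30.44 days.

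**1. Reproduce the plan's own figures.** 11 + 4 = Month 15, as in Table 1. Screening of about 1 month + 11 + 4 = 16 months, as in the synopsis. The timetable itself is coherent.

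**2. Count LFTs after a last dose at Month 11.**

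| Month | Months after last dose | In Table 1 | Status |
|---|---|---|---|
| 12 | 1 | yes | unconditional |
| 13 | 2 | no | no stated arrangement |
| 14 | 3 | no | no stated arrangement |
| 15 | 4 | yes | at Investigator discretion |

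If the monthly rule runs through the post-dose period, Section 10.5.1 implies 4 tests. Table 1 prints 2 of them (2/4 = 50%), and 1 is unconditional (1/4 = 25%). If the monthly rule covers the treatment period only, Months 13 and 14 drop out of the comparison. The conflict between required and discretionary testing remains at Month 15.

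**3. Interval between the two printed slots.** 3 × 30.44 = 91 days. With the visit windows, 91.3 − (4 + 14) = 73 to 91.3 + (4 + 14) = 109 days.

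**4. The 4-month limit.** The visit falls at 4 × 30.44 = 122 days after the last dose, with a window of 122 − 14 = 108 to 122 + 14 = 136 days. Section 11.2.2.2 requires strictly less than 4 months since discontinuation. If discontinuation is dated from the last dose, any visit on or after the nominal date fails that condition, whatever the Investigator thinks. Section 4.2 says within 4 months, so the two sections also differ at the boundary.

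**5. End of study.** Section 7.2 defines it for a subject as the last visit or the discontinuation visit, and for the study overall as the end of the 12-month follow-up of the last patient. If Section 4.2's sentence on routine practice uses the overall definition, it could take effect about 1 month after a Month 11 dose, leaving 3 of the 4 months in Section 10.5.1. If it uses the last visit, and that is the safety follow-up, it applies only afterwards. The text does not say which.

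**6. Where the data go.** SAP Section 5.4 uses the entire study period for safety. SAP Section 5.4.2 lists LFTs by subject and visit and summarises the incidence of ALT and/or AST at or above 3 times ULN by concurrent bilirubin elevation. SAP Section 4 does not impute. Tests not drawn are simply absent, and tests drawn on judgement count.

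**The case against.** The strongest case against has four parts.

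**A missing column is not a missing test.** Table 1 also has no columns for Months 2, 5, 7, 8, 10 and 11, yet LFTs are required monthly throughout treatment. Section 11.3.2 extends monthly sampling to time points without a scheduled visit, including draws by visiting nurses. This stands as a limit on the slot count. It does not close the gap, because the named off-visit months end at Month 11 and footnote 5 puts a condition on the follow-up period.

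**The monthly rule may apply to treatment only.** Section 10.5.1 can be read that way, with Section 4.2 setting the timing afterwards. This also stands. A reader might infer that half of the mandatory tests are missing; that holds only under the other reading.

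**Liver injury is still looked for.** A reader might infer that post-treatment hepatic injury goes unsought. The documents do not support that. Month 12 and the early discontinuation visit carry unconditional LFTs. Table 1 has adverse events recorded throughout, and serious events are followed to the end of the 4-month follow-up (Section 12.3.2). Jaundice calls for an LFT as soon as possible (Section 10.5.1), and LFTs after a suspension continue until resolution (Section 11.3.2). What remains exposed is mainly later elevation without symptoms.

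**The SAP plans little that could be distorted.** It has no LFT shift table (laboratory shift tables are in Protocol Section 13.5.2.4) and no separate post-dose analysis. So the claim that post-dose incidence and shifts become uninterpretable goes too far. Nor does the text say that only suspected cases would be tested; it speaks of what the Investigator deems appropriate. The narrower point survives: selectively obtained results enter the listings and one incidence summary.

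**Conclusion.** The inconsistency is real and concerns a safety rule: Sections 10.5.1 and 7.2 read as requiring post-treatment LFTs, while Section 4.2, footnote 5 and Section 11.2.2.2 make them discretionary. For a subject who takes every dose, one post-dose LFT (Month 12) is unconditional. The next slot is about 91 days later, conditional, remote, without a stated blood-draw arrangement, and possibly excluded by the wording of Section 11.2.2.2.

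This rests on a last dose at Month 11 and, for the 4-month limit, on dating discontinuation from the last dose. The absence of arrangements at Months 13 and 14 counts as a shortfall only if the monthly rule covers the post-dose period. Subjects stopped by the market withdrawal may have had their last dose in any month. The documents give neither those dates nor how they were then monitored, so the Month 12 to 15 count should not be applied to the approximately 30 enrolled subjects as a group.

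The consequence is uneven ascertainment of later symptom-free elevations, of unknown size. The sentence on routine practice is an ambiguity, not a demonstrated third rule.

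**What to change.** Reconcile Protocol Sections 4.2, 7.2, 10.5.1, 11.2.2.2 and Table 1 (including footnotes 4 and 5) into one governing statement on post-treatment LFTs. It should:

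- say whether the tests are required or discretionary;
- say whether the monthly rule extends past the last dose;
- use one reference date and one boundary for the 4-month period, compatible with the ±14-day visit window;
- say which end of study the routine-practice sentence means;
- show the time points in Table 1, with how blood is to be collected when the visit is remote.

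Which rule applies is for the sponsor's medical team.

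Because the study ended early, the abbreviated report should also state how many subjects had LFTs after the last dose, and at what times, beside the ALT/AST incidence summary.

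The cost is protocol and table wording, plus one short tabulation from data already planned for listing. Extra testing arises only if the required reading is adopted, and then only to carry out what Section 10.5.1 would already ask for.

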### 8.2. Exclusion Criteria

Candidates will be excluded from study entry if any of the following exclusion criteria exist during the screening period (28 days [+3 days] following the last dose of natalizumab):

1. Inability to comply with study requirements or, at the discretion of the Investigator, is deemed unsuitable for study participation.
2. Current participation in another investigational study.
3. Diagnosis of primary progressive, secondary progressive, or progressive relapsing MS (as defined by Lublin and Reingold) [Lublin 2014].
4. Females breastfeeding, pregnant, or planning to become pregnant; or women who have a positive pregnancy test result during screening.
5. History of drug or alcohol abuse (as defined by the Investigator) within 1 year prior to screening.
6. History of severe opportunistic infections (including PML) or any clinically significant, cardiac, endocrinologic, hematologic, hepatic, immunologic, metabolic, urologic, pulmonary, neurologic (other than MS), dermatologic, psychiatric, and renal, or other major disease, as determined by the Investigator.
7. Discontinued natalizumab due to suspicion of PML.

CONFIDENTIAL

The information contained herein may not be used, disclosed, or published without the written consent of Biogen MA Inc.

8. Known active malignancies (subjects with cutaneous basal cell carcinoma that has been completely excised prior to study entry remain eligible).
9. Clinically significant lab abnormalities revealed by blood tests at screening apart from those known to be associated with natalizumab (e.g., lymphocytosis).
10. Pre-existing hepatic disease or hepatic impairment, including ALT or AST at least 2 times the ULN (normal range for AST: 8 to 48 units per liter and for ALT: 7 to 55 units per liter). The normal range for liver enzyme levels may vary slightly by laboratory.
11. A history of autoimmune hepatitis or other autoimmune condition involving the liver.
12. The subject is using another MS therapy concomitantly.
13. Known history of human immunodeficiency virus (HIV).
14. Positive test result for Hepatitis C virus (test for hepatitis C virus antibody [HCV Ab]) or hepatitis B virus (test for hepatitis B surface antigen [HBsAg] and/or hepatitis B core antibody [HBcAb]). History of transplantation or any anti-rejection therapy.
15. Have had evidence of disease activity within the 6 months prior to screening visit defined as the following:
  - MS relapse, or

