### 11.3.2. Liver Function Test Assessments Prior to Daclizumab Dosing

Before a monthly dose of daclizumab is given, LFT results from prior testing performed within the previous 28 (+3) days must be reviewed by the Study Neurologist or their backup, and must be within protocol-required limits as described in Section 10.5.1.

LFTs can be performed as follows:

- Samples for LFTs must be drawn monthly and will be analyzed centrally for the purposes of this study. This includes any timepoints where there is not a scheduled

CONFIDENTIAL

The information contained herein may not be used, disclosed, or published without the written consent of  
Biogen MA Inc.

study visit and for samples which might be collected outside of the clinic (e.g., by visiting nurses). Accommodations will be made for LFT sampling and central testing for subjects choosing at-home dosing at Month 7, 8, 10 and 11.

- Results from either local or central LFT tests can be used for the medical management of the patient and to determine whether dosing should continue or be suspended at the monthly dosing timepoint (see Section 10).
- In any cases where LFTs are tested locally (e.g., at a local laboratory), samples must also be collected for central analysis for the purposes of this study.
- If the subject is administering daclizumab injections at home, site personnel must contact the subject after review of prior LFT results performed within 28 (+3) days to authorize the monthly injection, or if LFT results warrant, to instruct the subject to withhold their injection.
- LFTs following a treatment suspension must be performed through the central laboratory until the LFT abnormality has resolved. In cases where LFTs cannot be performed via central laboratory, repeat LFT results from local laboratory can be used for confirmation.

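### Protocol Section 10.5.1 gives the restart rule after a liver-enzyme suspension twice: once with either ALT or AST below 2 times ULN, once with both

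*Protocol*

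**What the plan says.** Protocol Section 10.5.1 lists triggers for temporary suspension, then a Note, then criteria for permanent discontinuation. The first trigger is ALT or AST above 3 times ULN.

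The second item in the trigger list is not a trigger but a restart condition: "ALT or AST have not exceeded 5 times the ULN; daclizumab may be resumed when ALT or AST have reached" a value below 2 times ULN.

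The Note gives the condition again: "After a suspension, dosing of daclizumab may be resumed when ALT/SGPT and AST/SGOT are" below 2 times ULN, "provided that the criteria for permanent discontinuation have not been met". One of those permanent criteria begins "Confirmed ALT or AST of" and sets the level at more than 5 times ULN. Another is ALT or AST above 3 times ULN together with total bilirubin above 2 times ULN. A second suspension for liver enzymes is also a permanent criterion, unless another cause is clearly identified.

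Section 11.3.2 makes this section the check before every monthly dose: recent results "must be within protocol-required limits as described in Section 10.5.1".

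**The concern.** The two restart statements join the enzymes differently, the bullet with *or* and the Note with *and*, and nothing in the section gives either one precedence. A site applying the bullet as written could re-dose a subject whose second enzyme is still above 2 times ULN. A site applying the Note would hold the dose on the same results.

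What is at stake is re-exposure to a drug with known liver-enzyme effects, and consistent handling across about 40 planned sites. The pre-dose check in Section 11.3.2 cannot settle the matter, because it sends the reader back to Section 10.5.1. The same check governs home doses at Months 7, 8, 10 and 11, which site staff authorize after reviewing the liver tests.

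**Working it through.** The plan gives no figure to reproduce. The check is to apply both sentences to the same results and see where the decisions part.

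**Inputs.** Exclusion criterion 10 in Protocol Section 8.2 prints the "normal range for AST: 8 to 48 units per liter and for ALT: 7 to 55 units per liter" and adds that ranges vary slightly by laboratory. So ULN is 55 U/L for ALT and 48 U/L for AST.

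**Thresholds.**
- 2 × ULN: ALT 2 × 55 = 110; AST 2 × 48 = 96 U/L.
- 3 × ULN: ALT 3 × 55 = 165; AST 3 × 48 = 144 U/L.

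**Rules as written**, for a first suspension, with neither enzyme ever above 5 times ULN and bilirubin not above 2 times ULN, so that no permanent criterion applies:
- Bullet: restart allowed if ALT < 2 × ULN *or* AST < 2 × ULN.
- Note: restart allowed if ALT < 2 × ULN *and* AST < 2 × ULN.

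**Decisions**, with a peak of 4 times ULN and retest values in multiples of ULN:

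| ALT | AST | Bullet | Note |
|---|---|---|---|
| 1.5 | 1.5 | restart | restart |
| 1.5 | 2.8 | restart | hold |
| 2.5 | 2.5 | hold | hold |

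**Example in units.** ALT 99 U/L is 99 / 55 = 1.8 times ULN. AST 120 U/L is 120 / 48 = 2.5 times ULN. The bullet is satisfied because 1.8 < 2. The Note is not, because 2.5 is not below 2. The suspension trigger does not decide the case, since neither value exceeds 3 times ULN.

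**Where the rules conflict.** If the second enzyme is above 3 times ULN, the trigger applies and dosing stays suspended whatever the bullet says. The conflict is therefore confined to one enzyme below 2 times ULN and the other from 2 to 3 times:
- ALT below 110 with AST 96 to 144 U/L, or
- AST below 96 with ALT 110 to 165 U/L.

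**Other places that might settle it.** Section 11.3.2 refers back to Section 10.5.1. Footnote 5 of Table 1 cites the product label for suspension and discontinuation and gives no restart rule. Section 10.1 tells sites "Refer to and follow the prevailing local labeling" and the Investigator Brochure, neither of which is available here.

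**The case against.** The strongest reply is that the bullet's *or* is loose shorthand. Read literally it would almost defeat the suspension: a subject with ALT at 4 times ULN and a normal AST already has one enzyme below 2 times. The authors more likely meant both enzymes, or whichever was raised. Both sentences are also permissive, so a site that waits for both enzymes complies with both, and the Study Neurologist or backup reviews the results before each dose. The local label may state the rule plainly.

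Much of this stands, and it is why the point is minor. It does not remove the inconsistency. Reading the bullet as *both* amounts to correcting it to match the Note. Reading it as *the enzyme that caused the suspension* still departs from the Note if that enzyme falls to 1.8 times ULN while the other stands at 2.5. The reviewing neurologist is told to apply the very section that is unclear.

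A reader might also infer a second contradiction: that the bullet forbids restart after any value above 5 times ULN, whereas the Note, through the permanent criteria, forbids it only after a confirmed one. The documents do not support that, for three reasons.
- The bullet says what may happen if 5 times ULN was not exceeded. When that condition fails it withholds its own permission and says nothing more. The Note is general and covers the case.
- The inference takes *or* in the 5-times clause to mean neither enzyme, while the conflict shown above takes *or* in the same sentence to mean either. Read literally throughout, the 5-times clause is met whenever one enzyme stayed at or below 5 times ULN.
- The protocol deliberately ties permanent discontinuation at this level to confirmation. Section 11.3.2 adds that, when the central laboratory cannot be used, "repeat LFT results from local laboratory can be used for confirmation".

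At most, the handling of an unconfirmed value above 5 times ULN is unclear between the two sentences.

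**Conclusion.** The *or*/*and* inconsistency is real and sits in the current text. It changes the dosing decision only when one enzyme is below 2 times ULN and the other is from 2 to 3 times. The U/L limits given above assume the protocol's printed ranges and shift with the laboratory's own. The conclusion also assumes that the bullet is read literally and that the label and Investigator Brochure do not override it. The two permanent criteria that run together in the text are taken as separate.

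Severity is minor. The documents give no frequency for this pattern of results, so neither harm to subjects nor a count of affected subjects can be inferred. The SAP (Sections 2 and 4) records that the study was terminated, with drug supply stopped, after about 30 subjects had enrolled. No endpoint, sample-size figure or analysis depends on this rule.

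**What to change.** Remove the restart text from the list of suspension triggers and keep a single rule in the Note: dosing may be resumed only when ALT and AST are both below 2 times ULN and no permanent-discontinuation criterion has been met, including a confirmed value above 5 times ULN.

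An unconfirmed value above 5 times ULN should follow the existing confirmation requirement. A new bar on restart after any such value should not be added: it would be a change of clinical policy and would undercut that requirement.

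The cost is an edit to the protocol wording, with no new tests and no change to the analysis. The downside is that some subjects would restart slightly later than the literal bullet allows. As the study has ended, the edit matters for any reuse of the text. For the study report, the by-visit liver listings planned in SAP Section 5.4.2 could be set against dosing dates to see whether any subject restarted in the conflict range.
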